### **Definition of Study Day:**

The number of study days relative to the first dose date of study drug (Study Day), is calculated as:

- Study Day = Date of assessment – Date of first dose of study drug +1, when the date of assessment is on or after the date of first dose of study drug
- Study Day = Date of assessment – Date of first dose of study drug, when the date of assessment is before the date of first dose of study drug

where the date of first dose of study drug is defined in Section 6.4.1

The day of the first dose of study drug is defined as Study Day 1, while the day before the date of first dose of study drug (i.e., Randomization visit) is defined as Study Day -1 (there is no Study Day 0).

For daily average pain scores assessed by NRS [REDACTED] any data captured in the e-diary up to 2am in the morning of the following day will be assigned to the previous day in the derivation of Study Day.

**Definition of Follow-up Day:**

The number of study days relative to the last dose date of study drug (Follow-up Day), is calculated as:

Follow-up Day = Date of assessment – Date of last dose of study drug

where the date of last dose of study drug up is defined in Section [REDACTED] 6.4.1

Follow-up Day will equal zero on the day of the last dose of study drug and positive values will indicate days during the follow-up period.

For daily average pain scores assessed by NRS [REDACTED] any data captured in the e-diary up to 2 am in the morning of the following day will be assigned to the previous day in the derivation of Follow-up Day.

**Definition of Treatment Period:**

Time from Study Day 1, through to Follow-up Day 4.

**Definition of Efficacy Follow-up Period:**

Time from Follow-up Day 5 through to Follow-up Day 28.

**Definition of Safety Follow-up Period:**

Time from Follow-up Day 5 through to Follow-up Day 30.

## **7.2 Study Population**

### **7.2.1 Disposition of Subjects**

The following subject data will be presented:

- Number of subjects with informed consent, discontinued during screening/wash-out, entered the baseline diary run-in, discontinued prior to randomization, randomized for all subjects with informed consent ('Total' overall only);
- Number and percentage of subjects who were randomized, took study drug, did not take study drug, in the analysis sets by treatment group and 'Total' over all treatment groups for all randomized subjects;
- Number and percentage of subjects who completed and discontinued the screening/wash-out, and primary reason for discontinuing screening/wash-out for all subjects with informed consent ('Total' overall only);
- Number and percentage of subjects who completed and discontinued prior to randomization, and primary reason for discontinuing prior to randomization for all subjects who came for randomization visit ('Total' overall only);

- Number and percentage of subjects who completed and discontinued treatment, and primary reason for treatment discontinuation by treatment group and ‘Total’ over all treatment groups for all randomized subjects, SAF and FAS;
- Number and percentage of subjects completed and discontinued the follow-up period, and primary reason for discontinuing the follow-up period by treatment group and ‘Total’ over all treatment groups for all randomized subjects and SAF;
- Number and percentage of subjects who completed and discontinued treatment at each visit, by primary reason for treatment discontinuation by treatment group and ‘Total’ over all treatment groups for all randomized subjects, SAF and FAS;
- Number and percentage of subjects excluded from PPS by reason for exclusion defined in Section 5.2.1 by treatment group and ‘Total’ over all treatment groups for FAS; and
- Number and percentage of subjects for each protocol version by treatment group and ‘Total’ over all treatment groups for randomized subjects, as well as, number and percentage of subjects for each protocol version for screen failures (subjects who discontinued during screening/wash-out, or prior to randomization) and Total Number of subjects enrolled (i.e. including Screen Failures).

A stacked bar plot of cumulative discontinuation rates (colored by primary reason for discontinuation) overall and at each visit by treatment group will be produced for the SAF.

### **7.2.2 Protocol Deviations**

Protocol deviations as defined in the study protocol (Section 8.1.6 Protocol Deviations) will be assessed for all randomized subjects. The number and percentage of subjects meeting any criteria will be summarized for each criterion and overall, by treatment group and total as well as by study site. Subjects deviating from a criterion more than once will be counted once for the corresponding criterion. Any subjects who have more than one protocol deviation will be counted once in the overall summary. A data listing will be provided by site and subject.

The protocol deviation criteria will be uniquely identified in the summary table and listing. The unique identifiers will be as follows:

- PD1 - Entered into the study even though they did not satisfy entry criteria,
- PD2 - Developed withdrawal criteria during the study and was not withdrawn,
- PD3 - Received wrong treatment or incorrect dose,
- PD4 - Received excluded concomitant treatment.

### **7.2.3 Demographic and Other Baseline Characteristics**

No hypothesis testing will be performed comparing treatment groups for demographic and other baseline characteristics.

### 7.2.3.1 Demographics

Demographic characteristics will be summarized by descriptive statistics for the following variables listed in [Table 15](#). This will be done for all randomized subjects, as well as for the SAF, FAS and PPS by treatment group and ‘Total’ over all treatment groups.

**Table 15 Demographic Characteristics**

Characteristic	Summarized as	Categories
Age (years)	Continuous	-----
Weight (kg)	Continuous	-----
Height (cm)	Continuous	-----
BMI (kg/m  )	Continuous	-----
Sex	Categorical	

● Male

● Female

● Unknown

Race	Categorical	

● White

● Black or African American

● Asian

● American Indian or Alaska Native

● Native Hawaiian or Other Pacific Islander

● Other

Ethnicity	Categorical	

● Not Hispanic or Latino

● Hispanic or Latino

Age group	Categorical	

● < 45 years

● ≥ 45 to < 65 years

● ≥ 65 years

EudraCT Age group	Categorical	

● ≥ 18 to ≤ 64 years

● ≥ 65 to ≤ 84 years

BMI group 1	Categorical	

● < 25 kg/m^2

● ≥ 25 to < 30 kg/m^2

● ≥ 30 kg/m^2

BMI group 2	Categorical	

● < 30 kg/m^2

● ≥ 30 kg/m^2

Number and percentage of subjects randomized in each site will be presented by treatment group and ‘Total’ over all treatment groups for randomized subjects. In addition, number and percentage of pooled sites and the combination of sites into pooled sites will be summarized by treatment group and overall for the FAS.

### 7.2.3.2 Fibromyalgia and Targeted Medical History

Fibromyalgia and targeted medical history will be summarized by descriptive statistics for the following variables listed in [Table 16](#). This will be done for all randomized subjects, the SAF, FAS and PPS by treatment group and ‘Total’ over all treatment groups.

**Table 16 Fibromyalgia Diagnosis and Targeted Medical History**

Characteristic	Summarized as	Categories
Time since FM diagnosis (years)	Continuous	-----
Time since onset of FM symptoms (years)	Continuous	-----
Currently treated for FM	Categorical	
 
● Yes
 
● No
 

History of Major Depressive Disorder (MDD) as assessed by M.I.N.I.	Categorical	
 
● Yes
 
● No
 

Ongoing MDD (only for subjects with a History of MDD)	Categorical	
 
● Yes
 
● No
 

Currently Treated with Medication for MDD (only for subjects with a History of MDD)	Categorical	
 
● Yes
 
● No
 

HADS Depression total score	Continuous	-----
HADS Depression group	Categorical	
 
● Normal (0 to 7)
 
● Mild mood disturbance (8 to 10)
 
● Moderate mood disturbance (11 to 14)
 
● Severe mood disturbance (15 to 21)
 

C-SSRS Item: 
 
● Suicidal ideation
 
● Suicidal behavior
 
● Suicidal ideation or behavior
 
● Self-injurious behavior without suicidal intent
 
	Categorical	
For each item:
 
 
● Yes
 
● No
 

History of Temporomandibular Disorders	Categorical	
 
● Yes
 
● No
 

History of Irritable Bowel Syndrome	Categorical	
 
● Yes
 
● No
 

History of Chronic Tension Type Headache	Categorical	
 
● Yes
 
● No
 

History of Migraine	Categorical	
 
● Yes
 
● No
 

History of Chronic Low Back Pain	Categorical	
 
● Yes
 
● No
 

History of Myalgic Encephalomyelitis/Chronic Fatigue Syndrome	Categorical	
 
● Yes
 
● No
 

Table continued on next page		

Characteristic	Summarized as	Categories
History of Interstitial Cystitis/Painful Bladder Syndrome	Categorical	
 
● Yes
 
● No
 

History of Endometriosis (Females Only)	Categorical	
 
● Yes
 
● No
 

History of Vulvodynia (Females Only)	Categorical	
 
● Yes
 
● No
 

Alcohol History	Categorical	
 
● Never
 
● Current
 
● Former
 

History of Alcohol Use Disorder (only for subjects with current or former Alcohol History)	Categorical	
 
● Yes
 
● No
 

History of Drug Use	Categorical	
 
● Never
 
● Current
 
● Former
 

History of Substance Use Disorder (only for subjects with current or former History of Drug Use)	Categorical	
 
● Yes
 
● No
 

First or Second Degree Family History of 
 
● Fibromyalgia
 
● Depression
 
● Bipolar disorder
 
	Categorical	For each Family History: 
 
● Yes
 
● No
 

CMSI: Complex Medical Symptom Inventory, C-SSRS: Columbia Suicide Severity Rating Scale, FM: Fibromyalgia, HADS: Hospital Anxiety and Depression Scale, MDD: Major Depressive Disorder, M.I.N.I: Mini-International Neuropsychiatric Interview, [REDACTED]

### 7.2.3.3 Fibromyalgia Related Baseline Disease Characteristics

Fibromyalgia related baseline disease characteristics will be summarized by descriptive statistics for the following variables listed in **Table 17**. This will be done for all randomized subjects, the SAF, FAS and PPS by treatment group and ‘Total’ over all treatment groups.

**Table 17 Fibromyalgia Related Baseline Disease Characteristics**

Characteristic	Summarized as	Categories
Baseline mean daily average pain score assessed by NRS	Continuous	-----
Baseline mean daily average pain score assessed by NRS group	Categorical	
 
● No pain: 0
 
● Mild: > 0 to < 4
 
● Moderate: <math>\geq 4</math> to < 7
 
● Severe: <math>\geq 7</math> to 10
 

WPI	Continuous	-----
SS scale score	Continuous	-----
Tender point count	Continuous	-----
PGIS	Categorical	
 
● No symptoms
 
● Very mild
 
● Mild
 
● Moderate
 
● Severe
 
● Very severe
 

*Table continued on next page*

Characteristic	Summarized as	Categories
CMSI total score at baseline	Continuous	
 
-----
 

Central pain etiology as defined by CMSI*	Categorical	
 
More centrally driven FM pain
 
Non-specific FM pain
 
More peripherally driven FM pain
 

FIQR:	Continuous	
 
-----
 

 
Function subscale
 
Symptoms subscale
 
Overall impact subscale
 
Total score
 
		

CMSI: Complex Medical Symptom Inventory, FIQR: Fibromyalgia Impact Questionnaire Revised, FM: Fibromyalgia; [REDACTED]

NRS: Numerical Rating Scale; PGIS: Patient Global Impression of Severity, SS: Symptom severity, WPI: Widespread pain index.

\* CMSI will be split into three groups using the CMSI total score at baseline: more centrally driven FM pain ( $\leq$  1st tertile); non-specific FM pain ( $>$  1st tertile to  $<$  3rd tertile) and more peripherally driven FM pain ( $\geq$  3rd tertile); [REDACTED]

#### 7.2.3.4 Medical History

Medical history is coded in Medical Dictionary for Regulatory Activities (MedDRA), and will be summarized by System Organ Class (SOC) and Preferred Term (PT) as well as by PT alone, by treatment group and “Total” over all treatment groups for the SAF.

#### **7.2.4 Previous and Concomitant Medications**

The following will be presented using the SAF:

- All previous medications prior to the baseline diary run-in
- All previous medications taken for any pain (i.e., FM pain only or FM pain and Other type of pain or Other type of pain only) prior to baseline diary run-in,
- All previous medications taken for FM pain (FM pain only or FM pain and Other type of pain) prior to baseline diary run-in,
- All previous medications during baseline diary run-in,
- All previous medications taken for any pain during baseline diary run-in,
- All previous medications taken for FM pain during baseline diary run-in,
- All concomitant medications during the double-blind treatment period,
- All concomitant medications taken for any pain during the double-blind treatment period,
- All concomitant medications taken for FM pain during the double-blind treatment period,
- All concomitant medications taken during the follow-up period,
- All concomitant medications taken for any pain during the follow-up period, and
- All concomitant medications taken for FM pain during the follow-up period.

Previous and concomitant medications are coded with World Health Organization Drug Dictionary (WHO-DD). Each of the above will be summarized by therapeutic subgroup (ATC 2nd level) and chemical subgroup (ATC 4th level) and preferred WHO name by treatment group and ‘Total’ over all treatment groups. Subjects taking the same medication multiple times will be counted once per medication and investigational period. A medication which can be classified into several chemical and/or therapeutic subgroups is presented in all chemical and therapeutic subgroups. All previous medications taken for any pain prior to the baseline diary run-in; all previous medications taken for any pain during baseline diary run-in; all concomitant medications taken for any pain during the double blind treatment period and all concomitant medications taken for any pain during the follow-up period will also be summarized by preferred WHO name by treatment group and ‘Total’ over all treatment groups.

In addition to the above summaries an overview of previous medications taken prior to the baseline diary run-in and previous medications during the baseline diary run-in taken to treat pain, will be produced. This will summarize the number and percentage of subjects in each of the following categories for each treatment group and ‘Total’ over all treatment groups:

- Any pain (i.e. FM pain only; or FM pain and Other type of pain; or Other type of pain only),
- FM pain (i.e. FM pain only; or FM pain and Other type of pain),
- FM pain only,
- FM pain and Other type of pain,

As with previous medication, concomitant medication (double-blind treatment period) and concomitant medication (follow-up period) taken to treat pain will be summarized for each treatment group and 'Total' over all treatment groups for the above categories.

The listing will only contain data of the subjects who actually used previous and concomitant medications.

### **7.2.5 Previous and Concomitant Non-Medication Therapy**

The following will be presented using the SAF:

- All previous non-medication therapies prior to baseline diary run-in,
- All previous non-medication therapies received for any pain (i.e., FM pain only or FM pain and Other type of pain or Other type of pain only) prior to baseline diary run-in,
- All previous non-medication therapies received for FM pain (FM pain only or FM pain and Other type of pain) prior to baseline diary run-in,
- All previous non-medication therapies received during baseline diary run-in,
- All previous non-medication therapies received for any pain during baseline diary run-in,
- All previous non-medication therapies received for FM pain during baseline diary run-in,
- All concomitant non-medication therapies received during the double-blind treatment period,
- All concomitant non-medication therapies received for any pain during the double-blind treatment period,
- All concomitant non-medication therapies received for FM pain during the double-blind treatment period,
- All concomitant non-medication therapies received during the follow-up period,
- All concomitant non-medication therapies received for any pain during the follow-up period, and
- All concomitant non-medication therapies received for FM pain during the follow-up period.

Each of the above will be summarized by treatment group and 'Total' over all treatment groups for:

- Normal Daily Exercise Routines,
- Chiropractic Care,
- Physical Therapy,
- Psychotherapy,
- Massage therapy, and
- Other.

Subjects receiving the same non-medication therapy multiple times will be counted once per medication and investigational period.

In addition to the above summaries an overview of previous non-medication therapies prior to the baseline diary run-in and previous non-medication therapies during the baseline diary run-in received to treat pain, the number and percentage of subjects with the following

categories will be summarized for each treatment group and ‘Total’ over all treatment groups:

- Any pain (i.e. FM pain only; or FM pain and Other type of pain; or Other type of pain only),
- FM pain (i.e. FM pain only; or FM pain and Other type of pain),
- FM pain only,
- FM pain and Other type of pain,

As with previous non-medication therapy, concomitant non-medication therapy (double-blind treatment period) and concomitant non-medication therapy (follow-up period) will be summarized for each treatment group and ‘Total’ over all treatment groups for the above categories.

The listing will only contain data of the subjects who actually used previous and concomitant non-medication therapies.

## **7.3 Study Drugs**

### **7.3.1 Exposure**

Duration of exposure will be summarized by treatment group and ‘Total’ over all treatment groups in three ways for the SAF:

- Descriptive statistics will be presented for the total number of days a subject was exposed to study drug.
- Number and percentage of subjects in each of the following mutually exclusive extent of exposure categories:
  - 1 to 7 days,
  - 8 to 14 days,
  - 15 to 28 days,
  - 29 to 48 days,
  - 49 to 64 days,
  - $\geq$  65 days
- Number and percentage of subjects in the following cumulative extent of exposure time categories:
  - $\geq$  1 day,
  - $\geq$  8 days;
  - $\geq$  15 days,
  - $\geq$  29 days,
  - $\geq$  49 days
  - $\geq$  65 days.

### **7.3.2 Treatment Compliance**

Overall compliance with the dosing schedule will be examined for subjects in the SAF whose total study drug count and first and last days of treatment are known.

Percent overall compliance will be summarized by treatment group and ‘Total’ over all treatment groups in two ways for the SAF:

- Descriptive statistics for percent overall compliance.
- Number and percentage of subjects in the following categories of percent overall compliance:
  - < 50%,
  - ≥ 50% to < 80%,
  - ≥ 80% to < 100%,
  - = 100%,
  - > 100% to < 120%,
  - ≥ 120%.

## 7.4 Analysis of Efficacy

Efficacy analyses will be performed using the FAS and the PPS where indicated. No formal hypothesis testing of comparison between treatment groups will be performed for the efficacy data during the follow-up period i.e., descriptive statistics will be used to summarize the continuous efficacy variables and frequencies and percentages will be used to summarize the categorical efficacy data.

### 7.4.1 Analysis of Primary Endpoint(s)

Analysis of the primary efficacy endpoint will be performed on the FAS and the PPS.

Table 18 describes the primary analysis and sensitivity analyses that will be performed for the primary efficacy endpoint.

**Table 18 Summary of the Primary and Sensitivity Analyses for the Primary Efficacy Endpoint**

Variable	Imputation	Analysis Set	Analysis Type
Change from baseline to Week 8 in mean daily average pain score assessed by NRS (Primary Analysis)	None	FAS	MMRM analysis of change from baseline a
Change from baseline to Week 8 in mean daily average pain score assessed by NRS (Sensitivity Analysis)	Discontinuation-reason based multiple imputation b	FAS	MMRM analysis of change from baseline a
Change from baseline to Week 8 in mean daily average pain score assessed by NRS (Sensitivity Analysis)	mBOCF c	FAS	ANCOVA analysis of change from baseline
Change from baseline to Week 8 in mean daily average pain score assessed by NRS (Sensitivity Analysis)	None	PPS	MMRM analysis of change from baseline a

aMMRM analysis uses data from baseline and change from baseline data at Week 1, Week 2, Week 3, Week 4, Week 5, Week 6, Week 7 and Week 8 time points.

bDiscontinuation-reason based multiple imputation (MI) will use a “Jump to Reference” algorithm (where placebo is the reference group) for subjects who discontinue due to lack of efficacy or AEs and standard regression-based MI for subjects with missing data for other reasons.

cmBOCF is defined as imputation by baseline observation carried forward for subjects who discontinue due to lack of efficacy or AEs, and imputation by last observation carried forward for subjects with missing data at Week 8 for other reasons.

#### 7.4.1.1 Primary Analysis of Primary Endpoint

The hypothesis for comparison of mean change from baseline between ASP8062 and placebo is shown below:

**H0:** The mean change from baseline to Week 8 in mean daily average pain score assessed by NRS (0 to 10 scale) for ASP8062 30 mg once daily group is same as (or higher, i.e., worse than) the placebo group.

**H1:** The mean change from baseline to Week 8 in mean daily average pain score assessed by NRS (0 to 10 scale) for ASP8062 30 mg once daily group is less than the placebo group.

The change from baseline in mean daily average pain score to Week 1, Week 2, Week 3, Week 4, Week 5, Week 6, Week 7 and Week 8 will be analyzed using a mixed-effect, repeated measures (MMRM) model including treatment, center (pooled where necessary), time (study Week 1 to 8), and treatment-by-time interaction as fixed effects, baseline mean daily average pain score and baseline mean daily average pain score-by-time interaction as covariates. The treatment group contrasts for change from baseline to Week 8 will be the primary statistical inference obtained from this model.

This analysis will utilize observed data, and there will be no imputation for missing data. Parameters will be estimated using restricted maximum-likelihood and the Kenward-Roger approximation will be used to estimate denominator degrees of freedom and adjust SEs.

An unstructured variance-covariance structure will be used to model the within-subject errors. If the fit of the unstructured covariance structure fails to converge, the following covariance structures will be tried in order until convergence is reached: heterogeneous Toeplitz (for efficacy endpoints captured in e-diary only, i.e. mean daily average pain score assessed by NRS [REDACTED] followed by compound symmetry.

Residual plots of scaled residuals will be used to check the fit of the model and assess whether there is any evidence of non-normality.

From the MMRM model the following results will be presented:

- Least squares (LS) mean estimates, SE and 2-sided 90% confidence interval (CI) for mean change from baseline to each analysis time-point (Week 1 to Week 8) within a treatment group (ASP8062, placebo),
- The difference in LS means for ASP8062 versus placebo, SE for the difference and 2-sided 90% CI for the difference at each analysis time-point,
- One-sided p-value for ASP8062 versus placebo at each analysis time-point, and
- Two-sided p-value for treatment-by time interaction.

An overlay plot will be provided for LS mean change from baseline from the MMRM analysis and mean change from baseline from the follow-up period +/- SE vs analysis time-point by treatment group.

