### **Statistical Methods:**

#### **Sample size justification:**

The sample size calculations are based on the primary efficacy endpoint of change from baseline to Week 8 in mean daily average pain NRS. A meta-analysis of the change from baseline in mean daily average pain NRS for pregabalin or duloxetine vs placebo in studies for fibromyalgia indicated an effect size of approximately 0.30.

Using an effect size of 0.39 (30% larger than the meta-analysis result) for the primary efficacy endpoint for the comparison of ASP8062 vs placebo, 84 subjects in the ASP8062 and placebo groups would be required to provide 80% power to demonstrate statistical significance using a 1-sided 5% significance level (based on the assumption of normally distributed data, and taking into account the interim analysis for futility).

The total number of subjects required for the analysis would be 168 (84:84 subjects in ASP8062: placebo). Assuming approximately 5% of randomized subjects will not contribute to the analysis, then a total of 178 subjects would be required for randomization using a 1:1 randomization ratio (89:89 subjects for the ASP8062: placebo groups).

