#### **7.4.1.1 Primary Analysis**

The primary analysis for the primary endpoint of change from baseline to Week 8 in the mean daily average pain NRS will use a mixed model repeated measures (MMRM) analysis, where the model will include the effects for treatment group, center (pooled where necessary), time (study Week 1 to 8) and treatment-by-time interaction, as well as the covariates of baseline mean daily average pain NRS and baseline pain-by-time interaction and subject as a random effect. The unconstrained between-time-point covariance structure will be used. If this is not feasible, additional covariance structures will be considered and details will be provided in the SAP. This analysis will utilize observed data, and there will be no imputation for missing data. The treatment group contrast for change from baseline to Week 8 will be the primary statistical inference obtained from the MMRM analysis. Least squares estimates for the primary endpoint will be shown for each treatment group, and for the treatment comparisons of ASP8062 vs placebo with 2-sided 90% confidence intervals. A one-sided 5% significance level will be used for the comparison involving ASP8062 vs placebo.

The hypothesis for comparisons is given as follows:

H0: The change from baseline to Week 8 in the mean daily average pain NRS for ASP8062 group is the same as (or worse than) the placebo group.

H1: The change from baseline to Week 8 in the mean daily average pain NRS for ASP8062 group is less than the placebo group.

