bDiscontinuation-reason based multiple imputation (MI) will use a "Jump to Reference" algorithm (where placebo is the reference group) for subjects who discontinue due to lack of efficacy or AEs and standard regression-based MI for subjects with missing data for other reasons.

cmBOCF is defined as imputation by baseline observation carried forward for subjects who discontinue due to lack of efficacy or AEs, and imputation by LOCF for subjects with missing data at the specific analysis time point for other reasons.

The following secondary binary response endpoints (responder, non-responder; as defined in Section 6.1.2) will be analyzed using the Fisher's exact test for ASP8062 versus placebo:

- Percentage of subjects achieving  $\geq 30\%$  (or  $\geq 50\%$ ) reduction from baseline to Week 8 in mean daily average pain score assessed by NRS where all subjects with missing Week 8 data are classified as non-responders,
- Percentage of subjects achieving  $\geq 30\%$  (or  $\geq 50\%$ ) reduction from baseline to Week 8 in mean daily average pain score assessed by NRS where mBOCF is used to impute a responder status for subjects with missing Week 8 data, and
- Percentage of subjects achieving  $\geq 30\%$  (or  $\geq 50\%$ ) reduction from baseline to EOT in mean daily average pain score assessed by NRS.

Summary statistics will show the number and percentage of subjects who show response for each treatment group, 2-sided 90% CI for the percentage within each treatment group (ASP8062, placebo) calculated using the exact unconditional approach, difference in

percentages, 2-sided 90% CI for ASP8062 versus placebo calculated using the exact unconditional approach, and 1-sided p-value. In addition, the above responder analysis will be repeated in the PPS as a sensitivity analysis of the percentage of subjects achieving  $\geq 30\%$  (or  $\geq 50\%$ ) reduction from baseline to Week 8 in mean daily average pain score assessed by NRS where all subjects with missing Week 8 data are classified as non-responders.

The following secondary endpoints will be analyzed using the MMRM analysis as described in Section 7.4.1.1 for the primary efficacy analysis (however with only analysis time-points Week 2, Week 4 and Week 8 included):

- Change from baseline to Week 2, Week 4 and Week 8 for the FIQR function, symptoms and overall impact subscales (where no explicit imputation is performed).

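### The last step of the MMRM covariance fallback (homogeneous compound symmetry with Kenward-Roger standard errors) miscalibrates the Week 8 test if it is ever reached and variance is not constant; a heterogeneous-variance last step costs little

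*SAP*

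**What the plan says.** The primary contrast is the treatment difference at Week 8 from an MMRM over Weeks 1 to 8 (SAP 7.4.1.1). On the error rate, Protocol 7.4.1.1 states: "A one-sided 5% significance level will be used for the comparison involving ASP8062 vs placebo". The protocol leaves any alternative covariance structures to the SAP, so the SAP's list is the controlling rule.

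SAP 7.4.1.1 starts with an unstructured matrix. On non-convergence it moves to heterogeneous Toeplitz, for e-diary endpoints only (the pain NRS is named), "followed by compound symmetry". Only the Toeplitz step is called heterogeneous, so the plain reading of the last step is one common variance and one common correlation. Some words are redacted just before that phrase. They follow the named e-diary endpoint, and I assume they do not name a further structure.

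Estimation is by REML, and the "Kenward-Roger approximation will be used to estimate denominator degrees of freedom and adjust SEs". No empirical standard error is specified at any step.

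SAP 7.4.2 carries the rule over to the FIQR subscales, which "will be analyzed using the MMRM analysis as described in Section 7.4.1.1 for the primary efficacy analysis", with Weeks 2, 4 and 8 only. FIQR is completed on the site tablet and not in the e-diary, so the Toeplitz step does not apply to it.

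**The concern.** With treatment-by-time and baseline-by-time terms in the model and complete data, the Week 8 estimate under compound symmetry is essentially the difference in Week 8 means, whatever covariance is assumed. The model-based standard error does depend on that assumption: compound symmetry replaces the Week 8 variance by the average over visits. Kenward-Roger corrects small-sample bias and degrees of freedom within the assumed structure; it does not repair a wrong variance model.

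If residual variance is larger at Week 8 than on average, the p-value and the 90% confidence interval are too favourable. If it is smaller, the test is conservative and power is lost. The same model serves the per-protocol and multiple-imputation sensitivity analyses (SAP Table 18), so those would inherit the problem instead of revealing it. A fallback exists for the case where the first choice fails, and it should be valid in that case.

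**Working it through.** **Reproducing the plan's design figure.** The synopsis (sample size justification) states: "Using an effect size of 0.39 (30% larger than the meta-analysis result) for the primary efficacy endpoint", and that "84 subjects in the ASP8062 and placebo groups would be required to provide 80% power to demonstrate statistical significance", one-sided at 5%, "taking into account the interim analysis for futility". The usual formula gives n per arm = 2 × (1.645 + 0.842)² / 0.39² = 81.3, so 82; the noncentral t also gives 82. The stated 84 is two more, which is compatible with a small futility allowance (its amount is not given). A two-sided 5% test would need 104, so the one-sided reading is right. For subjects who do not contribute, 84 / 0.95 = 88.4, so 89 per arm and 178 in all. The nominal level to protect is therefore one-sided 5%.

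**Complete-data calculation.** No weekly SDs or correlations appear in either document, so every SD path below is an assumption.

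- SE ratio (model SE / true SE) = √(mean of the visit variances / Week 8 variance)
- Actual one-sided alpha = 1 − Φ(1.645 × ratio)
- Actual coverage of the two-sided 90% interval = 1 − 2 × alpha

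Worked case, SD rising linearly 1.5-fold: with Week 1 SD set to 1, the eight squared SDs average 1.589 and the Week 8 variance is 2.25. The ratio is √(1.589 / 2.25) = 0.840, alpha is 1 − Φ(1.382) = 8.3%, and coverage is 83.3%.

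| Assumed SD path, Weeks 1 to 8 | SD8/SD1 | SE ratio | One-sided alpha |
|---|---|---|---|
| Linear fall | 0.8 | 1.128 | 3.2% |
| Flat | 1.0 | 1.000 | 5.0% |
| Linear rise | 1.1 | 0.955 | 5.8% |
| Linear rise | 1.25 | 0.902 | 6.9% |
| Linear rise | 1.5 | 0.840 | 8.3% |
| Linear rise | 1.75 | 0.798 | 9.5% |
| Linear rise | 2.0 | 0.768 | 10.3% |
| Rise to Week 4, then flat | 1.25 | 0.953 | 5.9% |
| Rise to Week 4, then flat | 1.5 | 0.925 | 6.4% |
| Rise to Week 4, then flat | 2.0 | 0.894 | 7.1% |

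FIQR illustration with three visits and assumed SDs of 1.3, 1.6 and 2.0: mean variance = (1.69 + 2.56 + 4.00) / 3 = 2.75; ratio = √(2.75 / 4.00) = 0.829; alpha = 8.6%.

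**Check by simulation with dropout.** REML compound-symmetry fits were simulated with 89 per arm, eight weeks, 12 pooled centers, a baseline-by-time term, 20% monotone dropout completely at random and 3,000 runs per case. A t reference with 300 df stood in for Kenward-Roger. Monte Carlo error is about 0.4 to 0.6 points.

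| True correlation | SD8/SD1 | SE ratio | One-sided alpha, model SE |
|---|---|---|---|
| AR(1), 0.9 | 1.0 | 0.95 | 5.7% |
| AR(1), 0.9 | 1.25 | 0.88 | 7.0% |
| AR(1), 0.9 | 1.5 | 0.82 | 9.1% |
| AR(1), 0.9 | 2.0 | 0.73 | 11.0% |
| Exchangeable, 0.7 | 1.0 | 1.01 | 4.7% |
| Exchangeable, 0.7 | 1.25 | 0.88 | 8.0% |
| Exchangeable, 0.7 | 1.5 | 0.81 | 9.2% |

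**After a change.** A structure with its own variance per visit returns the complete-data ratio to 1.00 and alpha to 5%. A sandwich standard error on the same compound-symmetry fits, without small-sample correction, gave 5.2% to 6.4% across the simulated cases.

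**The case against.** *Reach.* For the pain NRS, compound symmetry is two failures away. Heterogeneous Toeplitz already gives each week its own variance. The unstructured matrix has 8 × 9 / 2 = 36 parameters with 178 subjects planned; for FIQR it has 3 × 4 / 2 = 6. Nothing in the documents gives a probability of reaching the last step. This stands, and it sets the priority.

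*Convergence history.* A reader might infer from the SAP revision history, which records convergence trouble with this model, that the fallback is likely to be used. The documents do not support that. The trouble was attributed to the random subject effect, which is redundant beside an unstructured within-subject covariance and has been removed. Its removal makes the last step less likely.

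*Direction.* A reader might also take a growing variance as given. No passage says so. There is a reasonable argument for it: the model adjusts for baseline, and if weekly pain variance is stable while correlation with baseline decays, residual variance is proportional to 1 − ρ². Assumed correlations falling from 0.8 to 0.6 give an SD rise of √(0.64 / 0.36) = 1.33, and alpha of about 7.4% if linear. That makes a rise plausible without establishing it; flat and falling paths belong in the range.

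*Other safeguards.* The Week 8 ANCOVA with mBOCF, planned for both the NRS and FIQR, uses one value per subject, so its standard error does not depend on the repeated-measures covariance. An artificially small MMRM standard error might show up beside it. But it rests on a different missing-data assumption and would not correct the primary p-value.

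*Remedy.* Sandwich errors for every structure other than unstructured would give up Kenward-Roger under heterogeneous Toeplitz, where no inflation was shown. Nor does a sandwich error remove bias in the estimate from a wrong covariance when dropout is missing at random. Both points stand and narrow the fix.

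**Conclusion.** The last fallback step is poorly chosen, but the consequence is conditional twice over: the step must be reached, and the Week 8 variance must differ from the average over visits. Given both, with complete data, one-sided alpha runs from 3.2% (SD falling to 0.8) through 5.0% (flat) to 5.8% to 10.3% (linear rise of 10% to 100%), or 5.9% to 7.1% if a 1.25- to 2-fold rise stops at Week 4. Dropout with decaying correlation can push it somewhat higher, including to 5.7% at constant SD in the simulation. All sizes rest on assumed SD paths, and the simulation on dropout completely at random.

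A reader might conclude that the planned primary analysis has an inflated type I error. The documents do not support that: this variance-averaging mechanism is absent if unstructured converges, and also if heterogeneous Toeplitz does. FIQR is the more exposed case because it has no heterogeneous step in between, but it is a secondary endpoint with a small matrix. I rate this a low-priority contingency improvement.

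**What to change.** In SAP 7.4.1.1, replace the last step with a heterogeneous-variance structure (heterogeneous compound symmetry or heterogeneous AR(1)) for all MMRM endpoints, including FIQR, and keep Kenward-Roger. If homogeneous compound symmetry is retained as a final resort, specify an empirical (sandwich) standard error with a small-sample correction for that step only. Make the change before unblinding, so that the order is not chosen with p-values in view.

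The cost is one line of SAP wording and the matching code, plus a few covariance parameters. Heterogeneous compound symmetry has nine against two for the eight-week NRS, and four against two for FIQR. It would still impose a common correlation, so some misfit could remain with dropout and decaying correlation; heterogeneous AR(1) addresses that pattern more directly. The first-line analysis does not change.
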